7.3 Dietary Restrictions

There are no dietary restrictions on this protocol.

- 7.4 Prohibited Medications
 - Interferon therapy (e.g. Intron-A[®])
 - Anti-cancer directed therapy including chemotherapy with the exception of Avastin for treatment of pseudo-progression.
 - Allergy desensitization injections
 - Corticosteroid medications administered parenterally with the exception of corticosteroids treatment for treatment of pseudo-progression or treatment with inhaled, intranasal, ocular, or topical steroids. These cases should be discussed with the study chair.
 - Growth factors (e.g. Procrit[®], Aranesp[®], Neulasta[®])
 - Interleukins (e.g. Proleukin[®])
 - Other investigational medications
 - Illicit drugs
 - Any live / attenuated vaccine (e.g. varicella, zoster, yellow fever, rotavirus, oral polio and measles, mumps, rubella (MMR)) during treatment and until 100 days post last dose (**Stratum C only**).

Medications associated with prolonged QTc should be avoided. Please refer to Appendix G for a list. Because the lists of these agents change frequently, it is important to regularly consult frequently updated medical references. For the most current list of medications, please refer to the following reference:

Woosley, RL and Romero, KA, **www.Crediblemeds.org**, QTdrugs List, Accession Date December 2nd, 2016, AZCERT, Inc. 1822 Innovation Park Dr., Oro Valley, AZ 85755

8 Quality of Life Surveys

Health-related quality of life (HRQOL) is a construct based on the impact of health and illness on an individual's QOL, as assessed by dimensions of physical, psychological, and social health ¹. Several studies have shown that compared to healthy controls or other cancer survivors, survivors of pediatric brain tumors have the lowest HRQOL ^{2,3}. For example, children with brain tumors under active therapy are frequently viewed as socially isolated and/or often absent from school by their peers ⁴. Cosmetic effects of radiation or chemotherapy treatment (e.g. permanent or temporary alopecia) often occur ⁵, adding to social burdens and contributing to social isolation. Historically though, HRQOL measures have rarely been included as clinical trial endpoints ⁶⁻⁹. Fortunately, this trend is slowly changing.

Several criteria are considered when evaluating the utility of an HRQOL assessment tool. These include: reliability and validity of the measure in the population for which it is used, the option for use of proxy report, development and age appropriate versions as well as the inclusion of both a generic core (i.e. questions relevant in assessing the HRQOL of any sick child) and disease-specific modules (i.e. questions specific to brain tumor patients), costs of the study, and availability of forms in parents' native language ^{1,10}. An important note regarding HRQOL measures is that, though the option for parent or proxy reporting is typically necessary, self-report is preferred as parents may view the impact of the disease differently than the child ¹¹. Additionally, HRQOL measures should not be too generic. For this reason, HRQOL measures should include disease-specific modules to avoid missing clinically significant changes that are disease dependent ⁷. This approach might be particularly important in clinical trials where detecting even small changes related to an individual disease or treatment is necessary ¹².

There are several cancer-centric assessment tools that satisfy the criteria above ¹³⁻²⁰. The Pediatric Functional Assessment for patients with Brain Cancer (Peds-FACT-Br) is specific to children with brain tumors and English versions are free-of-charge, making this an attractive assessment tool for HRQOL. Unfortunately, there have been limited studies assessing its validity among different age groups ¹⁹.

Pediatric brain tumor survivors live with chronic neurocognitive effects. A core set of cognitive processes appears particularly affected in these children including attention, information processing speed, and working memory. With close monitoring of cognitive development, weaknesses can be readily identified so that appropriate interventions and support can be put in place. Within PNOC, we will focus on the validated measures described in Appendix H. See Appendix H for the references contained within this section.

9 Monitoring of Response

The blood draws performed at weeks 0, 12, 18, 24 and every 12 weeks thereafter at subsequent MRIs as part of immune monitoring will be used in the following two analyses.

- 9.1 Immuno-monitoring
- 9.2 Enzyme Linked Immuno-SPOT (ELISPOT) Assays

Frequencies of H3.3K27M-responsive T-lymphocyte precursors in peripheral blood mononuclear cells (PBMC) prior to and after administration of the K27M-peptide based vaccine can be measured by ELISPOT assay. The biological responses measured by ELISPOT will be done at the same time point at least for one individual participant to avoid inter-assay variability. Successful vaccination stimulates clonal populations of T cells that are capable of secreting cytokines in an antigen-specific, MHC-restricted fashion. We will utilize the ELISPOT assay to evaluate H3.3K27M-specific immune

responses of CD8⁺ T-cell populations as well as CD4⁺ T cells that react against the helper TT peptide. We will evaluate IFN- γ production to assess Type-1 T-cell response. Hence, even though our plans for peripheral blood drawing should provide us with sufficient PBMC to run both assays, if we still encounter a shortage of PBMC, IFN- γ ELISPOT will be prioritized over tetramer assays.

ELISPOT Assay: ELISPOT provides a measure of the induction of tumor-specific CD8⁺ and CD4⁺ T-cells by immunization. Blood specimens from the selected subjects will be obtained pre-, during and post-vaccination. ELISPOT assay will be performed to measure the frequency of a population of T cells capable of responding to the tumor specific antigen by secreting IFN- γ .

A subject will be considered to have responded, if at any of post-vaccine time point against the H3.3K27M antigen, the number of spots is double that at baseline, and there are at least 10 spots/20,000 cells, and if the number of the post-vaccine spots is at least three times the standard-deviation of the pre-vaccine value. This definition provides some protection against false positive response.

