6.2.3 Dose modification for Nivolumab

See Appendix I for management algorithms.

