Appendix I Management Algorithms

These general guidelines constitute guidance to the Investigator and may be supplemented by discussions with the Medical Monitor representing the Sponsor. The guidance applies to all immuno-oncology agents and regimens.

A general principle is that differential diagnoses should be diligently evaluated according to standard medical practice. Non-inflammatory etiologies should be considered and appropriately treated.

Corticosteroids are a primary therapy for immuno-oncology drug-related adverse events. The oral equivalent of the recommended IV doses may be considered for ambulatory patients with low-grade toxicity. The lower bioavailability of oral corticosteroids should be taken into account when switching to the equivalent dose of oral corticosteroids.

Consultation with a medical or surgical specialist, especially prior to an invasive diagnostic or therapeutic procedure, is recommended.

The frequency and severity of the related adverse events covered by these algorithms will depend on the immuno-oncology agent or regimen being used.

This page intentionally left blank

GI Adverse Event Management Algorithm

Rule out non-inflammatory causes. If non-inflammatory cause is identified, treat accordingly and continue I-O therapy. Opiates/narcotics may mask symptoms of perforation. Infliximab should not be used in cases of perforation or sepsis.

Patients on IV steroids may be switched to an equivalent dose of oral corticosteroids (e.g. prednisone) at start of tapering or earlier, once sustained clinical improvement is observed. Lower bioavailability of oral corticosteroids should be taken into account when switching to the equivalent dose of oral corticosteroids.

Renal Adverse Event Management Algorithm

Rule out non-inflammatory causes. If non-inflammatory cause, treat accordingly and continue I-O therapy.

Pulmonary Adverse Event Management Algorithm

Rule out non-inflammatory causes. If non-inflammatory cause, treat accordingly and continue I-O therapy. Evaluate with imaging and pulmonary consultation.

Patients on IV steroids may be switched to an equivalent dose of oral corticosteroids (e.g. prednisone) at start of tapering or earlier, once sustained clinical improvement is observed. Lower bioavailability of oral corticosteroids should be taken into account when switching to the equivalent dose of oral corticosteroids

Hepatic Adverse Event Management Algorithm

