Rule out non-inflammatory causes. If non-inflammatory cause, treat accordingly and continue I-O therapy. Consider imaging for obstruction.

Asymptomatic TSH elevation	 Continue I-O therapy per protocol If TSH < 0.5 x LLN, or TSH > 2 x ULN, or consistently out of range in subsequent cycles as clinically indicated; consider endocrinology or consider	2 sub: onsult	sequent measurem
Symptomatic endocrinopathy	 Evaluate endocrine function Consider pituitary scan Symptomatic with abnormal lab/pituitary scan: Delay I-O therapy per protocol 1-2 mg/kg/day methylprednisolone IV or PO equivalent Initiate appropriate hormone therapy No abnormal lab/pituitary MRI scan but symptoms persist: Repeat labs in 1-3 weeks / MRI in 1 month 		If improves (with without hormone replacement): • Taper steroids of month and con antibiotics for of infections • Resume I-O the • Patients with a insufficiency m continue steroi mineralocortico
Suspicion of adrenal crisis (e.g. severe dehydration, hypotension, shock out of proportion to current illness	 Delay or discontinue I-O therapy per protocol Rule out sepsis Stress dose of IV steroids with mineralocorticoid activity IV fluids Consult endocrinologist If adrenal crisis ruled out, then treat as above for symptomatic endocrinopathy 		

Endocrinopathy Adverse Event Management Algorithm

Rule out non-inflammatory causes. If non-inflammatory cause, treat accordingly and continue I-O therapy. Consider visual field testing, endocrinology consultation, and imaging.

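### Section 7.4 bars parenteral corticosteroids without an exception for immune-related toxicity, yet Appendix I lists intravenous steroids, with no oral option, for suspected adrenal crisis on nivolumab

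*Combined protocol and SAP*

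**What the plan says.** Section 7.4 (Prohibited Medications) applies to every stratum unless an item says otherwise. Its steroid item prohibits "Corticosteroid medications administered parenterally with the exception of corticosteroids treatment for treatment of pseudo-progression or treatment with inhaled, intranasal, ocular, or topical steroids" and then adds: "These cases should be discussed with the study chair".

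Section 6.2.3, on dose modification for nivolumab, consists of one instruction: "See Appendix I for management algorithms". Appendix I describes its own standing with the words "These general guidelines constitute guidance to the Investigator". On steroids it states: "Corticosteroids are a primary therapy for immuno-oncology drug-related adverse events". Intravenous dosing is its reference route, with a limited oral alternative: "The oral equivalent of the recommended IV doses may be considered for ambulatory patients with low-grade toxicity".

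The endocrinopathy algorithm in Appendix I has two rows that matter here. For symptomatic endocrinopathy with an abnormal laboratory result or pituitary scan it gives "1-2 mg/kg/day methylprednisolone IV or PO equivalent". For suspected adrenal crisis it gives "Stress dose of IV steroids with mineralocorticoid activity" and no oral equivalent.

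**The concern.** The section on prohibited drugs forbids a treatment that the protocol's own nivolumab toxicity plan calls for. Section 1.1 reports that immune-mediated events in the paediatric nivolumab trial were similar to those seen in adults. Such events are therefore foreseeable in Stratum C, whose only primary objective is safety.

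Three consequences are realistic:

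- a site meets contradictory instructions in an emergency;
- time is lost while someone checks the protocol or contacts the study chair;
- correct treatment is logged as use of a prohibited medication, among the deviations that Section 10.3 has reviewed weekly.

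Most clinicians would probably follow Appendix I, so it is not suggested that treatment would be withheld.

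**Working it through.** The main check is a comparison of texts. A small calculation then shows the scale.

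**1. What 7.4 permits.** The exceptions are pseudo-progression and four local routes (inhaled, nasal, eye and skin). Local routes do not deliver systemic rescue, so pseudo-progression is the only ground on which 7.4 allows a systemic parenteral steroid. Oral steroids are not barred by this item.

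**2. What Appendix I asks for.**

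| Situation in Appendix I | Route given | Can a site also comply with 7.4? |
|---|---|---|
| Low-grade toxicity, ambulatory patient | Oral equivalent may be considered | Yes, by using the oral route |
| Symptomatic endocrinopathy, abnormal result or scan | Intravenous or oral | Yes, by using the oral route |
| Suspected adrenal crisis | Intravenous only | No |

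The general oral option does not rescue the third row. It is limited to ambulatory patients with low-grade toxicity, whereas the examples in that row include hypotension and shock.

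**3. Whether another section settles it.**

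- Section 6.2.3 points to Appendix I but does not say that it overrides 7.4.
- Section 9.7 requires suitable medical care for all adverse events but does not mention 7.4.
- The adrenal crisis row has immunotherapy held or stopped. A patient whose treatment is only held may stay on protocol, and 7.4 does not lift its bar during a hold.
- The study-chair sentence in 7.4 follows the listed exceptions and does not name immune-related toxicity.

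No section adds the exception or states an order of precedence.

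**4. Limits of what can be shown.** Most of the other algorithm diagrams are not visible in the copy reviewed. Notes under the gastrointestinal and pulmonary algorithms refer to patients already on intravenous steroids, so that route is expected there too. An intravenous-only step can be demonstrated only for suspected adrenal crisis.

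**5. Scale.** The planned numbers in Section 3.1 are 19 (Stratum A), 10 (Stratum B) and 20 (Stratum C).

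- Total: 19 + 10 + 20 = 49.
- Share given nivolumab: 20/49 = 0.408, or 41%.

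The documents give no rate *p* of suspected adrenal crisis, so the values below are assumptions. Expected cases are 20*p*, and the chance of at least one case is 1 − (1 − *p*)^20.

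| Assumed *p* | Expected cases in 20 | Chance of at least one |
|---|---|---|
| 0.5% | 20 × 0.005 = 0.1 | 1 − 0.995^20 = 0.095 |
| 1% | 20 × 0.01 = 0.2 | 1 − 0.99^20 = 0.182 |
| 2% | 20 × 0.02 = 0.4 | 1 − 0.98^20 = 0.332 |

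At every assumed rate, zero cases is the most likely outcome.

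**The case against.** The strongest reply is that a sensible reading resolves the matter. Section 7.4 is a general list for all strata, while 6.2.3 and Appendix I deal specifically with nivolumab toxicity, and the specific text should prevail. Section 9.7 points the same way. Immunotherapy is already being held or stopped in this situation, and a clinician facing possible shock will treat. This is probably how it would go in practice. But the protocol states no such rule of precedence, and Appendix I calls itself guidance, which weakens it against a flat prohibition.

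Two further points concern the consequences. The study-chair sentence says only that discussion should happen, not that it must come first, so delay is possible but not mandated. Nor does any section say that a breach of 7.4 is recorded as a deviation; the deviation wording in Section 9.9 concerns procedures for serious adverse events. Both points stand: delay and a recorded deviation are plausible inferences, not stated outcomes.

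Finally, the demonstrated conflict is one row of one table, the event is rare, and the rates are assumed. All of that is accepted. It limits the weight of the point but leaves the contradiction in place.

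**Conclusion.** The point holds: 7.4 is wrong as written. Followed literally, it bars a rescue step that the protocol's own nivolumab algorithm calls for, and no other section supplies the exception. This should be fixed.

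The demonstrated conflict is confined to suspected adrenal crisis in Stratum C. Under assumed rates of 0.5% to 2%, it has a 10% to 33% chance of arising at least once. Confidence is high on the wording and lower on the practical consequences, which are inferred.

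No effect is claimed on regimen-limiting toxicity counts, the stopping boundary, adverse event grading or the efficacy analyses. The intention-to-treat population in Section 10.3.1 contains everyone enrolled, so a recorded deviation would remove nobody.

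**What to change.** Extend the steroid exception in Section 7.4 with wording such as: *or, in Stratum C, treatment of immune-related adverse events per Appendix I; emergency use does not require prior discussion with the study chair.*

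The second half is needed because a newly added exception would otherwise fall under the existing sentence that sends excepted cases to the study chair.

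The cost is one clause in 7.4. It needs no new visit, procedure, data item or patient, and no change to the analysis.

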9.2.1 Tetramer Analysis of K27M-reactive T cells in Participant's PBMC

Tetramer analyses allow us to evaluate the presence of H3.3K27M-specific CD8⁺ T-cells in peripheral blood with a great sensitivity without *in vitro* re-stimulation of the cells. It is expected, that significant (a log or more) increase in the frequency of peptide-responsive CD8⁺ T cells will be observed in some, but not all, patients immunized with tumor-antigen based vaccines. In an exploratory manner, these PBMCs will also be evaluated for surface expression of an integrin receptor very late antigen (VLA)-4, which has been implicated to confer T-cell homing to CNS tumors²⁸ and chemokine receptors (e.g. CXCR3 and CCR5).

CD8⁺ cells from PBMC will be positively selected on immunobeads (this procedure is established and available at UCSF). The enriched CD8⁺ cell fraction will be tested by flow cytometry for the percentage of cells expressing CD8 surface antigen.

In addition to CD8, VLA-4 ($\alpha_4\beta_1$ integrins) and LFA-1 expression on tetramer-positive T cells will be examined as markers dictating preferential homing to the brain tumor sites.

Tetramer assays will be done with PBMC samples obtained at baseline and specified time points after vaccinations. We will define a single time-point positive response for a peptide to be (1.5 + B)% of all CD8⁺ cells positive by tetramer assay, where B is the percent positive at baseline, which is usually less than 0.1%. In analogy to the definition of ELISPOT response, a patient will be considered to have responded if he/she has two consecutive single time-point responses for the K27M peptide. Response rates will be reported as for ELISPOT.

Flow cytometric analyses of lymphocyte subsets

Number of CD4⁺, CD8⁺ T cells as well as CD4^{+/}Foxp3⁺ T regulatory cells at serial time points pre- and post-vaccines will be evaluated. These data will be evaluated in an exploratory manner.

9.2.2 Evaluation of Primary and Recurrent Tumor Tissues

We will evaluate H3.3K27M expression in the patients' available tumor tissues (either pre-vaccine or after progression post-vaccines; or both) by immunohistochemistry (IHC) and reverse transcriptase-polymerase chain reaction (RT-PCR).

If tumors recur following vaccinations, it will be critical to evaluate how tumors escape the effects of vaccines. To this end, we will evaluate the following specific issues as much as the tissue-availability allows:

- Antigen-loss: We will assess, using IHC and RT-PCR, whether the recurrent tumors express H3.3K27M.
- Immune cell infiltration: One reason tumors may escape a vaccine-induced immune response is through the failure of reactive T cells to infiltrate the tumor. To examine this, whenever freshly resected tumor tissues (not fixed or frozen) or fresh or flash frozen are available, we will isolate tumor infiltrating lymphocytes (TILs) and characterize their numbers, phenotype, and antigen-specificity using HLA-A2 tetramers for H3.3K27M. Using multi-color flow-cytometry, we will also determine the function and viability of tetramer⁺ TILs by staining for perforin/IFN-γ and Annexin-V, respectively. Control tissues will include pre-vaccine tumors (if available) and recurrent tumors from patients not in the vaccine trial. These studies will allow us to evaluate whether vaccine-induced T-cells efficiently traffic to the brain tumor site and maintain their function and viability.

9.3 Evaluation of Efficacy (or Activity)

Immunotherapeutic approaches for children with gliomas are a relatively new era and therefore we have limited experience on how to monitor response. Recently the Immunotherapy Response Assessment in Neuro-Oncology (iRANO) working group has proposed guidelines on how to monitor and assess efficacy in adult brain tumor patients treated with immunotherapy as a development of the iRANO criteria, that were established to better account for the phenomenon of pseudo-progression in adult patients ^{34,35}. The pediatric neuro-oncology working group (RAPNO) is currently working on their guidelines for response criteria for pediatric neuro-oncology patients³⁶. Our limited experience with immunotherapies have shown that early radiological changes could be misinterpreted as progression due to therapy induced inflammation and long-term benefit can still be seen even after initial progression or even after the appearance of new lesions ^{14,37}. The response criteria are adapted from iRANO.

9.3.1 Antitumor Effect

9.3.1.2 Definitions

Evaluable for toxicity

All patients will be evaluable for toxicity from the time of their first treatment with the study therapy.

Evaluable for objective response

Only those patients who have measurable disease present at baseline, have received at least one dose of the vaccine and Poly-ICLC in combination with nivolumab, and have had their disease re-evaluated will be considered evaluable for response. These patients will have their response classified according to the definitions stated below. (Note: Patients who exhibit objective disease progression prior to week 12 at the first scheduled MRI will also be considered evaluable.)

9.3.1.3 Disease Parameters

In order to completely document the assessment of response, the two-dimensional tumor measurements for all target lesions upon which the assessments of tumor response are based should be explicitly noted in the radiology report for the baseline and all subsequent follow-up exams. Reports for the follow-up exams should reiterate the measurements obtained at baseline for each target lesion. Newly occurring lesions should also be enumerated in these reports, and changes in lesions should be described.

Tumor response criteria for this study are to be determined by changes in size using the maximal 2dimensional cross-sectional tumor measurements, T x W (product of the longest diameter of the tumor [width (W)] and its longest perpendicular diameter [transverse (T)], using either T1 or T2 weighted images (which ever gives the best estimate of tumor size). This will allow comparison with historical studies as outlined in the statistical design section, such as CCG-9941, ACNS0126, ACNS0927 and ADVL1217 which used cross-sectional measurements in their determination of response status.

The following section describes the methodology.

1. For MRI imaging, the longest diameter can be measured from the axial plane or the plane in which the tumor is best seen or measured, provided the same plane is used in follow ups.

2. The longest measurement of the tumor (or width, W) should be determined.

3. The 2 perpendicular measurements should be determined (transverse (T) measurement-perpendicular to the width (W) in the selected plane

Measurable disease

Measurable disease is defined as the lesions (or lesions) that can be accurately measured in at least 2 dimensions by MRI (no less than double the slice thickness).

All tumor measurements will be recorded in millimeters or decimal fractions of centimeters.

Target lesions

All measurable lesions up to a maximum of 5 lesions total representative of all involved areas should be identified as target lesions and recorded and measured at baseline. Target lesions will be selected on the basis of their size (largest) and their suitability for accurate repeated measurements.

Non-measurable disease

Non-measurable disease is all other lesions (or sites of disease), including leptomeningeal disease.

Methods for Evaluation of Measurable Disease

All measurements will be taken and recorded in metric notation using a ruler or calipers. All baseline evaluations will be performed as closely as possible to the beginning of treatment.

The same method of assessment and the same technique will be used to characterize each identified and reported lesion at baseline and during follow-up.

